**I. Purpose, Background and Rationale**

**A. Aim and Hypotheses**

Nearly 9 out of 10 chronic obstructive pulmonary disease (COPD) deaths in the United States (US) are attributed to smoking. Most (>90%) smokers with COPD are interested in quitting but success rates are very low; only about 12% are able to quit with FDA-approved medications as part of a clinical trial and far fewer (<5%) quit following brief advice to quit. An alternative approach for smokers who cannot or will not quit with first-line therapies is tobacco harm reduction, or transitioning smokers to potentially less harmful products (e.g., e-cigarettes). E-cigarettes (ECs), when used consistently and exclusively, help smokers quit and reduce tobacco-related harms. This is particularly true for smokers with COPD who report significant reductions in COPD exacerbations, improved lung function, and quality of life after switching to ECs. However, the extent of harm reduction is directly related to the degree of switching (i.e., reduction in CPD). Most smokers who transition to ECs make a partial switch to EC (i.e., dual users) and, while they experience harm reduction benefits relative to continued smoking, the benefit is less than those who completely switch. To reduce harm among high-risk smokers with COPD who are unable to quit with first-line therapies, there is an urgent need to understand how training smokers on the optimal EC puff pattern can be optimized to facilitate a complete or predominant pattern of EC use among smokers with COPD. The alternative for these smokers is continued smoking of, arguably, the most harmful tobacco product on the market and imminent disease progression.

Our long-term goal of our research is to decrease tobacco-related disease burden among high-risk smokers unable to quit using standard methods. The overall objective of this application is to evaluate the impact of EC training on changes in puff patterns, nicotine craving and exposure, cigarette smoking, and improvements in COPD-related health effects among smokers with COPD who have been unable to quit smoking using pharmacotherapy. Our central hypothesis is that training on optimal puff behavior with ECs (compared to brief advice to switch to ECs) will result in a greater proportion of patients predominantly using ECs and a greater reduction in COPD-related health effects. Furthermore, greater dose of intervention will result in amplified effects. Our central hypothesis has been formulated on the basis of our preliminary data, which suggest that 1) smokers with COPD have a particularly difficult time quitting, 2) smokers with COPD have high levels of interest in using ECs, and 3) predominant EC users engage in distinct puff patterns compared to continued smokers; this puff pattern can be 'trained' and results in higher rates of switching to EC.

Smokers with COPD, stratified by EC naïve and current dual users, who are unwilling to make a pharmacotherapy-assisted quit attempt but that are willing to use ECs will be randomly assigned to receive 1) brief advice to switch to ECs at baseline, 2) a single session of training on optimal EC puffing and use at baseline, or 3) enhanced EC training on optimal EC puffing and use at baseline, day 3, and wks 4, 8, and 12. Participants will complete a human laboratory assessment of EC use patterns and a complementary 12-week RCT of real-world smoking and EC use patterns. The human lab trial will be conducted over two visits to assess acute changes in puff patterns and nicotine craving and exposure. The RCT will provide real-world data on changes in cigarette smoking, COPD-related health effects, and EC puff patterns.

1. Our specific aims are:

**Aim 1:** Understand differences in acute (i.e., in-lab) changes in puff patterns (i.e., puff duration), cigarette craving, and nicotine exposure from pre- to post-EC training/brief advice between smokers who received brief advice versus EC training (single episode and enhanced EC training arms combined). Smokers who receive EC training will show greater increases in puff duration compared to brief advice (*H1a*), greater reductions in cigarette craving compared to brief advice (*H1b*), and greater increases in nicotine exposure compared to brief advice (*H1c*).

**Aim 2:** Determine the longer-term impact of EC training and training dose on switch patterns (i.e., % predominant EC users), health effects (i.e., changes in cardiovascular health, functional activity, lung function) and puff patterns. In a dose response pattern, enhanced EC training will result in the greatest proportion of predominant EC users at Wk12 (*H2a*), the greatest improvements in health outcomes at Wk12 (*H2b*), and the greatest increases in puff duration from baseline to Wk12 (*H2c*) followed by single session training and brief advice.

## B. Background and Significance

### **Cigarette smoking among patients with chronic obstructive pulmonary disease (COPD):**

**(COPD):** Over one third of smoking-related deaths are a result of COPD and up to 90% of COPD cases are caused by smoking. COPD is associated with profoundly reduced quality of life due to symptoms including wheezing and sleep disturbance. Therefore, the benefits of quitting smoking and symptom reversal are enormous for this population. Despite these potential benefits, about 40% of patients with COPD continue to smoke. The majority of smokers with COPD report interest in quitting smoking but when offered pharmacotherapy, only 12-14% succeed in a sustained quit, indicating that smokers with COPD have a very difficult time quitting.

### **Electronic cigarettes (ECs) and tobacco harm reduction for smokers with COPD:**

Evidence indicates that ECs are less harmful compared to combustible cigarettes. In their consensus statement, the National Academies for Science, Engineering, and Medicine concluded that there is “conclusive evidence” that completely switching to ECs reduces smokers’ exposure to toxicants carcinogens, or cancer-causing substances. While there are no long-term studies of cancer risk due to EC use, mounting evidence from in vivo and in vitro studies suggests reduced cancer risk from ECs compared to cigarettes. For smokers that are unable or unwilling to quit combustible smoking, the question is whether ECs offer a reduction in harm (not elimination of harm) compared to cigarettes. For smokers that are unable or unwilling to quit nicotine and tobacco use, completely switching to ECs likely reduces their cancer-risk. Moreover, smokers with smoking attributable diseases, like COPD, who already experience a heightened risk due to continued smoking, may experience the greatest benefit from making a complete switch from combustible cigarettes to ECs. In randomized trials, ECs have resulted in better quit rates compared to control and NRT. In a prospective, non-randomized study of COPD smokers who switched to ECs or continued smoking, EC users showed a significant reduction in COPD exacerbations and

improvements in lung function and measures of quality of life. These data indicate ECs may be a promising harm reduction tool for smokers with COPD that have been unable to quit.

**Factors associated with successful switching:** One primary factor that predicts successful switching is EC puff behavior. The experience of vaping differ significantly from the experience of smoking cigarettes, resulting in a learning curve to achieve sufficient nicotine delivery. Cross-sectional studies of exclusive EC users indicate that they are able to extract more nicotine from ECs compared to naïve or dual users. Existing research shows that smokers who successfully switch to ECs take longer puffs compared to those who only partially switch, suggesting that smokers who are successful in switching naturally learn how to effectively puff on an EC. It remains unknown whether smokers can be trained on optimal puff behavior.

### C. Rationale

[figure not shown]
Studies by our team^13 and others show that smokers who achieve predominant or exclusive EC use have unique puff patterns compared to continued smokers (i.e., greater puff duration). Smokers who switch to ECs and become predominant or exclusive EC users adapt their puff patterns within 1 week by taking longer, slower puffs. While no studies have examined methods for training smokers on optimal topography, one study showed that a slight variation in instructions to switch resulted in reduced smoking.

This study is innovative in the following ways. First, the study will enroll a high-risk population of smokers that is not only understudied but stands to experience marked improvements in health and quality of life from quitting smoking. The alternative for these smokers is continued smoking of the most harmful tobacco product on the market and imminent disease progression. Second, the concept of providing training on optimal use of ECs is innovative. Despite evidence that those who successfully switch to ECs show distinct topography patterns compared to EC “failures”, no studies have attempted to train on optimal use. This strategy pulls from the NRT literature and posits that a similar form of training on “optimal” use will increase EC effectiveness of facilitating switching and reduce smokers’ tobacco-related harm.

### D. ECs and E-liquid

The Evolv Reflex EC (Figure 1) will be used for the proposed study. Our team has conducted three validation studies with the device and embedded software. It is both a highly effective EC and a topography device that tracks and stores all facets of information about the participant’s use of the product, including puffing topography which we view as a great strength. See Figure 2 for an example of the topography feedback provided by the device. The device has the capacity to store 4 weeks of data between in-person visits. We will use the eScribe topography software available specifically for this device. In addition, we

Figure 2. Example topography

will use a secondary topography device (eTop device) during in-person lab-based visits in order to correlate topography from the two devices. Our team has used the eTop device in numerous past trials. The Reflex device is a pod-based device and is compatible with nicotine salt and freebase nicotine e-liquid. We will use commercially available nicotine salt e-liquid in 5% nicotine concentration. The e-liquid has been tested by Drs. [name] and [name] at KUMC Department of Internal Medicine to independently confirm the e-liquid concentration is within 1% of the advertised levels. We considered other concentrations but chose 5% because it is the most commonly used concentration among

Figure 1. Reflex EC

market leaders like JUUL, has demonstrated high appeal and cigarette-like levels of nicotine delivery among smokers, and high rates of switching. For the human lab portion of the study, participants will be provided a pre-filled pod for each visit. For the RCT, we will provide pre-filled pods in 4-week increments. If participants cannot tolerate the Evolv Relfex, we will offer a choice of JUUL or Vuse devices. JUUL and Vuse are pod based systems. We will offer menthol or tobacco flavors in 5% or 3% concentration.

[figure not shown]
## II. Research Plan and Design

**A. Study Objectives:** The overall objective of this application is to evaluate the impact of EC training on changes in puff patterns, nicotine craving and exposure, cigarette smoking, and improvements in COPD-related health effects among smokers with COPD who are unable to quit smoking using pharmacotherapy.

**B. Study Type and Design:** The proposed study is an open label randomized clinical trial of EC training and training dose among smokers with COPD. Smokers with COPD (n=45) stratified by EC use history (naïve vs. current use) will be randomized (1:1:1) to receive brief advice to switch to ECs, single session EC training, or enhanced EC training. Participants will complete an in-lab assessment of pre-intervention EC puff patterns followed by intervention and a follow-up assessment of resultant changes in EC puff patterns. Visits will be separated by a standard minimum 24-hour washout period. Participants will complete a final assessment of EC puff patterns at Wk 12. Immediately following completion of the second human lab visit, participants will receive 12 weeks of EC and assistance with switching, based on treatment allocation. Participants will complete in-person follow-up assessments throughout the 12-week switch period and those in the enhanced training arm will receive ongoing training.

Participants will remain abstinent from nicotine/tobacco for 12 hours prior to each study visit. Abstinence will be verified by eCO (>12 ppm. Self-report will be used for EC abstinence, as there is currently no objective, reliable measure to verify non-use of these products within the time the participants will be in the lab. Participants will be provided the device of their choice with either tobacco or menthol flavored e-liquid or pods. Participants will puff ad libitum for 30 minutes to establish baseline levels. Throughout the session, puff topography will be measured. Blood sampling for changes in nicotine levels will occur at -5 minutes (pre-vaping session) and +30 minutes (immediately post-session). At the end of Human Lab Visit 1, participants will receive training on the EC based on intervention allocation. Human Lab Visit 2 will be identical to Visit 1 but will not include additional EC training. Human Lab Visit 3 (~Wk 12) will be identical to Visit 2 and will measure longer-term changes in EC puff patterns. The Evolv Reflex EC has the capacity to track and store 4 weeks of data about a participant's use of the product and puffing topography between in-person visits. eScribe topography software will be used for the device. The JUUL and Vuse devices do not collect data. Because daily use of EC is consistently one of the best predictors of exclusive EC use, we will reinforce this pattern across sessions within the enhanced EC training arm and problem-solve barriers related to daily use.

**Figure 1:** Overall study flow

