**Dual Users:**

Use of tobacco products other than cigarettes and e-cigarettes in the past 30 days, current use of cessation medications, pregnant, planning to become pregnant, or breastfeeding, recent history of cardiovascular or pulmonary events in the past 3 months, household member current or previously enrolled in the study

3. Withdrawal/Termination criteria:

Participants will be instructed to present to the lab nicotine deprived (12 hours abstinent) for the first study visit. If participants present to the first study visit with an eCO  $>12$  ppm or they report other nicotine use on two separate study visits, they will be withdrawn from the study (i.e., participants will be rescheduled one time).

4. Participants will not be allowed to participate in another research study that aims to alter their tobacco use during this research study.

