## 2. Study Procedures:

- a. **Initial Screening:** The initial screening will review inclusion/exclusion criteria by phone or online screener. Those eligible will be scheduled to complete an in-person visit within 14 days.
- b. **Final Screening (Day 0):** Participants will be instructed to smoke and vape as they normally would before the final screening. Final eligibility screening will be conducted in-person and will consist of a pregnancy test, exhaled carbon monoxide (eCO), providing evidence of EC use (bring EC to visit; dual users only), and obtaining informed consent. Participants will complete carbon monoxide (CO) measurement to confirm current smoking status (CO > 12 ppm). CO is collected by a simple, non-invasive breath test that involves the participant holding their breath for ~15 seconds and then exhaling into a straw connected to the CO monitor. Cigarette smoking will be assessed using the Timeline Followback (TLFB) in which individuals report on number of cigarettes per day (CPD) in the past 7 days. To assess baseline self-reported respiratory health, participants will complete the COPD assessment test (CAT). The modified Cigarette Evaluation Scale (mCES) will assess subjective effects and sensory experiences at the end of the session. Participant's intentions for future use (e.g., purchase, use) of ECs will be assessed using a 4-item measure. Participants will sample two e-liquid flavors (Menthol and Tobacco) to establish preference. Participants will go home with their device and e-liquid of choice to practice at home. Participants will complete baseline measures. Participants will be compensated \$10 for the final screening.

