- c. **Human Lab Visit 1 (1-14 days after Final Screening):** At Human Lab Visit 1, participants will be re-screened according to inclusion/exclusion criteria. Pregnancy exclusion will be confirmed at each visit. They will be instructed to remain nicotine abstinent for 12 hours prior to the visit. Participants will complete CO measurement to confirm tobacco/nicotine abstinence. Participants will be provided with an overview of the study, and complete additional baseline self-report measures. Self-report will be used for EC abstinence, as there is currently no objective, reliable measure to verify non-use of these products within the time the participants will be in the lab. Cigarette smoking will be assessed using the TLFB in which individuals report on number of CPD in the past 7 days. Participants will be provided the device of their choice and pre-filled pod of their preferred e-liquid flavor. Participants will puff ad libitum for 30 minutes to establish baseline topography levels. Throughout the session, pre-intervention puff topography will be measured via a pressure sensor attached to the device/product and by the integrated topography software within the EC. This will not require anything additional of the participant. Blood sampling for changes in nicotine levels will occur at -5 minutes (pre-vaping session) and +30 minutes (immediately post-session). Self-reported levels of cigarette craving and withdrawal will be measured

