- e. **Between Week 0 and Week 4:** Participants will be provided with the device of their choice and pre-filled pods to use between visits for the real-world switch period. If chosen, the Evolv Reflex EC device will collect and store 4 weeks of data on the participant's EC use patterns and puffing topography. The JUUL and Vuse devices do not collect data. Research staff will conduct a brief phone check in with all participants on their switch date. During this call, a trained research assistant will assess tobacco and nicotine use since the last visit and will briefly trouble shoot barriers to switching to the e-cigarette.
- f. **RCT Visit – Week 4:** At Week 4 topography data will be downloaded from the EC and reviewed. In addition, participants will return their used and unused pods which will be weighed to assess e-liquid consumption between visits. Those in the Brief Advice and Single Session Training arms will not receive additional training. For those in the Enhanced Training arm, they will receive additional real-time feedback on their puff patterns. This arm is intended to mimic the level of support provided to smokers making a quit attempt using traditional quit smoking strategies and to determine the minimum level of support necessary to achieve a pattern of predominant EC use. Our approach with this arm is intentionally flexible to match the needs of each participant over the course of behavior change. For the purposes of rapport-building and continuity of care, attempts will be made to have participants meet with the same staff member each session. For participants in all study arms, the following will be done. Topography will be used to objectively and passively measure EC puff patterns. Participants will again complete eCO measurement to confirm smoking status. Cigarette smoking will be assessed using the TLFB in which individuals report on number of CPD in the past 7 days. To

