assess changes in self-reported respiratory health, participants will complete the CAT. Lung function will be assessed via spirometry. Self-reported levels of cigarette craving and withdrawal will be measured using the Tiffany-Drobes QSU-brief and MNWS. The mCES will assess subjective effects and sensory experiences at the end of each session. Participant's intentions for future use (e.g., purchase, use) of ECs will be assessed using a 4-item measure. At the end of the visit, participants will be provided another 4-week supply of pre-filled pods and encouraged to continue their switch. Participants will be compensated \$20 for this visit.

- g. **Between Week 4 and Week 8:** Participants will be provided with another 4-week supply of pre-filled pods to use between visits for the real-world switch period. The Evolv Reflex EC device will collect and store 4 weeks of data on the participant's use and puffing topography. The JUUL and Vuse devices do not collect data.
- h. **RCT Visit – Week 8:** Procedures at the Week 8 the visit will closely mirror Week 4 visit. Used and unused returned pods will be weighed. Topography data will be downloaded and reviewed. Those from the Enhanced EC Training study arm that have not achieved optimal topography or predominant EC use will receive real-time feedback on their puff patterns. Participants will again complete eCO measurement to confirm smoking status. Cigarette smoking will be assessed using the Timeline Followback (TLFB). To assess changes in self-reported respiratory health, participants will complete the CAT. Lung function will be assessed via spirometry. Self-reported levels of cigarette craving and withdrawal will be measured using the Tiffany-Drobes Questionnaire on Smoking Urges – brief (QSU-brief) and Minnesota Nicotine Withdrawal Scale (MNWS). The modified Cigarette Evaluation Scale (mCES) will assess subjective effects and sensory experiences at the end of each session. Participant's intentions for future use (e.g., purchase, use) of ECs will be assessed using a 4-item measure. Participants will be compensated \$20 for this visit.
- i. **Between Week 8 and Week 12:** Participants will again be provided with 4 weeks of pre-filled pods to use between visits for the real-world switch period. The Evolv Reflex EC device will collect and store 4 weeks of data on the participant's use and puffing topography. The JUUL and Vuse devices do not collect data.

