- j. **RCT Visit – Week 12:** Participants will smoke and vape as they normally would. Participants will complete eCO measurement to confirm smoking status. Because the eCO is the only measure needed for this visit, visit location will be flexible. Visits will be conducted as determined by location and abilities of the study participant. Participants will be compensated \$10 for this visit.
- k. **Human Lab Visit 3:** Human Lab Visit 3 (Week 12) will be identical to Visit 1 (above) but will not include any training. The visit is intended to measure longer-term changes in EC puff patterns. Participants will be instructed to remain abstinent from nicotine and tobacco for 12 hours prior to the study visit. Participants will complete eCO measurement to confirm tobacco/nicotine abstinence. To assess changes in self-reported respiratory health, participants will complete the CAT. Lung function will be assessed via spirometry. Self-reported levels of cigarette craving and withdrawal will be measured using the Tiffany-Drobes QSU-brief and MNWS. The mCES will assess subjective effects and sensory experiences at the end of each session. Participant's intentions for future use (e.g., purchase, use) of ECs will be assessed using a 4-item measure. At the end of the visit, a 6-minute walk distance (6MWD) test will be done to assess the participant's overall ability to conduct everyday activities. Baseline cardiovascular functioning will be measured using Pulse Wave Velocity, a sensitive measure of arterial stiffness that shows rapid (~1 month) changes with switching to ECs. Baseline beat-to-beat blood pressure will be measured to assess blood pressure and vascular elasticity. Participants will be compensated \$50 for this visit.

- I. Monthly for 3 months post active study completion – phone follow up with participant.
3. Due to COVID-19 and the need to keep patients and researchers safe, we may use Zoom, a HIPAA compliant, university approved video conferencing software, during the visit. This will allow the participant to smoke freely (unmasked) while the researcher can watch and communicate with the participant via video conferencing from outside the clinic room. We will only enter the room when necessary and will ensure the participant is masked when research staff are present.
4. All procedures, tests, and visits are being performed solely for research purposes and are not billable to insurance.

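### The blanket 12-hour abstinence rule contradicts two visit descriptions and leaves the Week 4 and Week 8 eCO unable to confirm smoking status if it is followed as written

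*Protocol*

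**What the plan says.** The general rule is in the Protocol, section II.B (Study Type and Design): "Participants will remain abstinent from nicotine/tobacco for 12 hours prior to each study visit".

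The visit-level text in section II.E.2 is more specific, and it varies:

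- **Final screening (item b):** "Participants will be instructed to smoke and vape as they normally would before the final screening".
- **Human Lab Visit 1 (item c):** "They will be instructed to remain nicotine abstinent for 12 hours prior to the visit". Visit 2 is described as identical apart from training and some tests. Visit 3 repeats the 12-hour instruction.
- **Week 4 and Week 8 RCT visits (items f and h):** "Participants will again complete eCO measurement to confirm smoking status". Neither item says whether participants should abstain or smoke as usual beforehand. Both items also list the QSU-brief and MNWS for craving and withdrawal.
- **Week 12 RCT visit (item j):** "Participants will smoke and vape as they normally would. Participants will complete eCO measurement to confirm smoking status".

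The withdrawal criteria in section II.D.3 give a third scope: "Participants will be instructed to present to the lab nicotine deprived (12 hours abstinent) for the first study visit".

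eCO has two roles in section II.E.1. Under Human Laboratory Assessments, a fall of more than 50% from initial screening marks compliance with 12 hours of abstinence. Under RCT Assessments, eCO is the biochemical check on smoking status, and a value below 6 ppm indicates a complete switch. Cigarette counts come from the 7-day TLFB.

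**The concern.** An eCO reading can check a report of not smoking only if the participant was free to smoke beforehand. If staff ask for 12 hours without tobacco and then measure eCO, a low value may show only that the instruction was followed. It does not show whether the person has stopped smoking.

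At final screening and the Week 12 RCT visit, the visit-level text contradicts the general rule, and a reader can take the specific text as governing. At Weeks 4 and 8 there is no such text. Staff who follow section II.B literally would impose abstinence at two visits where eCO is supposed to corroborate the TLFB. The Background says that most smokers who take up e-cigarettes become dual users, and these are the people eCO most needs to separate from complete switchers. Craving and withdrawal at those visits would also be scored in a deprived state. If some staff applied the rule and others did not, the scores would not be comparable between participants.

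**Working it through.** **1. Scope of the rule, visit by visit**

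| Visit | Section II.B rule, read literally | Visit-level text | Stated purpose of eCO |
|---|---|---|---|
| Final screening | abstain | usual use | confirm current smoking (above 12 ppm) |
| Human Lab Visits 1 and 2 | abstain | abstain | confirm abstinence |
| Weeks 4 and 8 | abstain | silent | confirm smoking status |
| Week 12 RCT visit | abstain | usual use | confirm smoking status |
| Human Lab Visit 3 | abstain | abstain | confirm abstinence |

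Two rows contradict the rule outright. In the Weeks 4 and 8 row, the rule is the only instruction and it works against the stated purpose.

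**2. Does a study visit mean only a lab visit?** The inclusion criteria require willingness to complete six in-person study visits. There are three human lab visits, and Visit 2 doubles as Week 0. Adding final screening gives 3 + 1 = 4. At least 6 − 4 = 2 of the six must therefore be RCT visits, so the protocol does use the term for them.

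**3. What 12 hours of abstinence could do to the reading.** The 6 ppm cut-off comes from RCT Assessments and the 12 hours from section II.B. The documents give no CO half-life, so it is an assumption here, varied from 2 to 12 hours.

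- Fraction remaining = 0.5^(12/half-life)
- Highest usual level that falls to the 6 ppm cut-off = 6 / fraction remaining

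| Assumed half-life (h) | Fraction remaining | Usual eCO below which the reading is under 6 ppm | Reading for a smoker usually at 20 ppm |
|---|---|---|---|
| 2 | 0.016 | 384 ppm | 0.3 ppm |
| 3 | 0.062 | 96 ppm | 1.2 ppm |
| 4 | 0.125 | 48 ppm | 2.5 ppm |
| 5 | 0.189 | 31.7 ppm | 3.8 ppm |
| 6 | 0.250 | 24 ppm | 5.0 ppm |
| 8 | 0.354 | 17 ppm | 7.1 ppm |
| 12 | 0.500 | 12 ppm | 10.0 ppm |

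The last row corresponds to a fall of exactly 50%, the edge of the protocol's compliance marker. There, a smoker usually at 13 ppm reads 13 × 0.5 = 6.5 ppm and is not mistaken for a switcher. Participants enter above 12 ppm, so in that row only someone who has since cut down is affected. With shorter half-lives, many smokers at their entry level would also read under 6 ppm.

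**4. Which planned results use these readings.** Aim 2, the sample size section (II.C) and the analysis section (V.A) place the switching outcome at Week 12. None of them plans a Week 4 or Week 8 switch proportion.

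**The case against.** The best defence is context. The sentence opens a paragraph about lab sessions: 30 minutes of ad libitum puffing, blood at −5 and +30 minutes, then Human Lab Visits 1 to 3. Abstinence is repeated in the visit text only for lab visits. The withdrawal criteria say first study visit where Human Lab Visit 1 must be meant, so the term is used loosely. The author may well have meant lab visits only. This stands as a reading of intent, but it does not remove the conflict in the text, because the same term covers RCT visits in the inclusion criteria and the Week 4 and 8 items are silent.

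A reader might infer stronger claims. The documents do not support them:

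- **That the Week 12 switch outcome is misclassified, or that its classifying eCO is unknown.** The Week 12 RCT visit measures eCO under usual use to confirm smoking status, and Human Lab Visit 3 measures it to confirm abstinence. The stated purposes distinguish the two readings.
- **That Week 4 and Week 8 switch rates are inflated.** No such rate is a planned estimate. One person is 1/15 = 6.7 percentage points of an arm, but that shift attaches to nothing the protocol plans to report.
- **That the Enhanced arm would receive a different intervention.** At Week 8, those "that have not achieved optimal topography or predominant EC use will receive real-time feedback on their puff patterns". The condition names no eCO criterion, and the 6 ppm cut-off defines a complete switch, not predominant use.
- **That 12 hours always halves eCO, so a low reading makes a smoker a switcher.** The 50% fall is a compliance marker, not a stated effect in everyone. The TLFB would still record the rest of the week's cigarettes.

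**Conclusion.** The inconsistency is real and minor. The section II.B rule contradicts the final screening and Week 12 RCT visit descriptions, and it is the only pre-visit instruction that reaches Weeks 4 and 8. If it is applied there, eCO loses its value as a biochemical check on the TLFB, and craving and withdrawal are measured under imposed abstinence.

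The size of the eCO problem depends on a half-life the documents do not give. The usual level below which a continuing smoker reads under 6 ppm is about 24 to 48 ppm for half-lives of 6 to 4 hours, and 12 ppm for a half-life of 12 hours. All of this also assumes that staff follow section II.B literally at those two visits. No planned estimate, and no part of intervention delivery, is shown to be affected.

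**What to change.** Reconcile the passages:

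1. In section II.B, limit the 12-hour abstinence instruction to Human Lab Visits 1 to 3.
2. In section II.E.2, items f and h, state that the Week 4 and Week 8 RCT visits take place under usual smoking and vaping, as the Week 12 RCT visit item already does.
3. Optionally, in RCT Assessments, tie the 6 ppm rule to the eCO taken at the RCT visits.

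The cost is protocol wording and participant instructions. No visit, measurement or analysis is added.
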